In order to further evaluate the utility of DCR as a tool for assessment of baseline respiratory physiology, it is important to be able to compare it with real time conventional pulmonary function tests such as spirometry. Previous studies have compared sequential lung function testing to dynamic x-ray images; even if attempting a maximal effort there will be significant variability in 2 separate manoeuvres (i.e when sequentially performing a dynamic x-ray and then contiguously a spirometry). Currently there have been no studies which compare a dynamic chest x-ray with a simultaneous lung function study such as spirometry.

This study will therefore address this issue using performing simultaneous spirometry and DCR. Therefore one key aim of the study would be to establish how DCR compares with spirometry in a healthy population of individuals.

We would seek to also perform the DCR with simultaneous spirometry in a cohort of CF patients. DCR and spirometry are already performed as part of the annual review process. As highlighted DCR is generally well tolerated by pwCF. Spirometry can be physically or psychologically more challenging for pwCF. By performing simultaneous spirometry and DCR it would allow for a comparison with the healthy control group. This would provide the second aim of the Study to understand how we can relate DCR to pwCF's Spirometry.

Finally, as mentioned above DCR has become part of our annual review process in LHCH since 2019. The annual review process seeks to capture the clinically relevant information needed to assess the overall health of pwCF. By further analysing these DCR films with the other metrics of annual review process we may better understand how DCR relates to lung health over time. For example, are there any features of DCR which will predict future outcomes for pwCf. This study will therefore explore the relationship between longitudinal changes in DCR and key clinical measures of CF.

Aims:

1. Measure lung function via spirometry with simultaneous DCR in healthy controls
2. Measure lung function via spirometry with simultaneous DCR in pwCF
3. Investigate the relationship between spirometry and DCR in healthy controls, CF, and compare these two cohorts.
4. Investigate the relationship between DCR imaging and key clinical markers of CF recorded in the annual review process.

Null hypothesis: there is no relationship between parameters recorded by DCR and that of conventional spirometry in healthy individuals

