Retrospective Review of longitudinal DCR data with regards to clinical markers of CF status

Aim: To see how changes in key quantitative markers from DCR imaging relate to key CF clinical parameters

Study design: pwCF consenting for part B of the study will also be consented for using their current imaging as part of a longitudinal review of DCR imaging. Analyses will include an evaluation of the relationship between baseline DCR quantitative measurements and key clinical CF parameters that are recorded as part of their ongoing monitoring and care.

Schedule of Events

Below is highlighted a timetable for the schedule of events.

Table 1 – Schedule of Events for Healthy Volunteers

Contact	Purpose	Event	Duration
1	Indirect Contact	Individual contacts study team following poster campaign	N/A
1	Initial Direct contact	Provided with patient information sheet and consent information	20 minutes
2	Consent	Informed Consent taken	20 minutes
3	Attendance for imaging	Dynamic chest radiograph acquired with spirometry Completion of questionnaire	30 minutes

Table 2 – Schedule of Events for people with CF

Contact	Purpose	Event	Duration
1	Indirect Contact	Contacted via letter, patient information sheet enclosed	N/A
1	Initial Direct contact	Ensure provided with patient information sheet and consent information	20 minutes
2	Consent	Informed Consent taken	20 minutes
3	Attendance for imaging	Dynamic chest radiograph acquired with spirometry Completion of questionnaire	30 minutes

Once recruited the individual will attend for radiology department for the acquisition of the imaging and spirometry.

Dynamic chest X-ray procedure with paired spirometry

This study involves performing 2 simultaneous investigations – Dynamic x-ray and Spirometry, outlined below. For both parts of the Study A and B the process will be the same.

Spirometry:

Spirometry will be performed using validated and accredited spirometers that are used in clinical practice. The Study would utilise Geratherm® Spirostik™ spirometers (which can be Bluetooth or not) and documented using Geratherm® Blue Cherry™ software.

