- Current exacerbation

Spirometry exclusion criteria (same as for Group A, see above)

Statistical analysis

Statistical analysis will be carried using the R software package, produced and supported by the R Foundation for Statistical Computing, under the GNU GPL v2 public license.

All data will be collated electronically and stored on a secure server in line with data protection.

Two-sided P-values of <0.05 will be considered as statistically significant. Confidence intervals will be presented where appropriate and feasible.

Comparison of the data will be primarily between dynamic chest x-ray results and spirometry data. Depending on the distribution of the dataset, paired t-tests or the relevant non-parametric equivalent will be used to analyse within groups. Categorical data will be presented as frequency and percentage. Continuous data will be presented as number of observations, mean, standard deviation, median and interquartile range as appropriate.

Proposed timetable of events

- **December 2022** – Start of Protocol write up.
- **January 2023** – research proposal submission to local research committee
- **March 2023**- Sure group review and revisions to protocol and study literature
- **July 2023** -Iras application
- **September 2023 to September 2024** - Data collection is projected to take around 365 days, aiming for completion end of July 2023. This allows for the recruitment of 2 ‘healthy volunteers’ and 2 people with CF a week.
- **September to October 2024**- Data analysis
- **October/November/December 2024**- write up of research results +/- publication

Figure 3 – Gantt Chart of Projected Timetable December 2022 – December 2024

Task	D	J	F	M	A	M	J	J	A	S	O	N	D	J	F	M	A	M	J	J	A	S	O	N	D
Protocol Write up	█	█	█	█	█	█	█																		
R&I committee meeting LHCH		█																							
Sure Group review				█	█	█	█																		
Iras Application							█	█	█																
Study period										█	█	█	█	█	█	█	█	█	█	█	█	█	█	█	
Data analysis																						█	█		
Results write up																							█	█	█

Safety

Ionising Radiation

This study requires exposure to ionising radiation.

We are exposed to radiation in our daily lives and our annual average radiation exposure in the UK is 2.7mSv

An example of typical radiation doses from clinical investigations are included below.

Table 4 - Effective Doses for Common Radiological Examinations

Projection	Estimated effective dose (mSv)
Chest PA	0.014
Chest lateral	0.038

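### Part C asks how changes in DCR relate to CF markers, but its one named analysis uses baseline DCR and no stated method can relate change to a marker

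*Combined protocol and SAP*

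**What the plan says.** The aim of Part C is "To see how changes in key quantitative markers from DCR imaging relate to key CF clinical parameters". The rationale, under 'DCR as an assessment of pulmonary function', says the same: "This study will therefore explore the relationship between longitudinal changes in DCR and key clinical measures of CF". Numbered Aim 4 is broader and does not mention change: "Investigate the relationship between DCR imaging and key clinical markers of CF recorded in the annual review process".

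The Part C study design names one analysis: "Analyses will include an evaluation of the relationship between baseline DCR quantitative measurements and key clinical CF parameters". The sentence goes on to say that these parameters come from patients' continuing clinical follow-up. It does not say which film is the baseline, when the parameters are read, which DCR measure or marker leads, or what method is used.

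The Statistical analysis section does not mention Part C. It says "Comparison of the data will be primarily between dynamic chest x-ray results and spirometry data", and its only inferential method is that "paired t-tests or the relevant non-parametric equivalent will be used to analyse within groups". Correlation appears in the hypotheses, but only for DCR against spirometry.

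On the films, the rationale says "DCR has become part of our annual review process in LHCH since 2019". The Part B study design notes that DCR and spirometry are done separately at routine annual review. In Part B the film is taken during the third spirometry attempt. The Part C design says "pwCF consenting for part B of the study will also be consented for using their current imaging as part of a longitudinal review", and Recruitment Part B says that the Part B investigation will be used in the longitudinal review. No section says how the two kinds of film are combined.

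**The concern.** An analyst who followed only the named analyses would relate baseline DCR to clinical parameters and run paired tests. Neither step answers the stated question about change. The analysis of change would then be chosen after the data had been seen, with at least five DCR measures (section 'Dynamic Chest X-ray'), unnamed markers, and a two-sided 0.05 threshold.

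The second, weaker part concerns the Part B film. It enters a series of films acquired in a different way. Part B is said to add no radiation, so the film probably stands in for that year's routine film and would usually be the patient's latest. If filming during a spirometry manoeuvre shifts DCR values, the shift would coincide with the end of follow-up and could be mistaken for change within the patient.

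**Working it through.** The plan gives no sample size, effect size or power for Part C, so there is no figure of its own to reproduce. The first step compares the texts. The remaining steps are illustrations.

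**1. Question against method.**
- The aim needs change in DCR set against a marker.
- The Part C analysis supplies baseline DCR set against a marker.
- The Statistical analysis section supplies a test of a mean paired difference.
- Nothing supplied matches the aim.

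**2. Can a paired test stand in?** Assumptions: 100 patients (the Part B target), mean DCR change 0.3 SD, 4,000 simulated datasets, two-sided 0.05.

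| True correlation of DCR change with marker change | Paired t-test rejects | Correlation test rejects |
|---|---|---|
| 0 | 84% | 5% |
| 0.3 | 85% | 86% |
| 0.6 | 85% | 100% |

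The paired test carries no information about the relationship.

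**3. Can baseline correlation stand in?** This step takes the reading in which DCR and marker come from the same visit. Assumed model: DCR has between-patient variance 0.8 and visit variance 0.2. The marker has between-patient slope B on DCR, within-patient slope W, and residual variance 0.5 + 0.2 = 0.7. Then

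r = (0.8B + 0.2W) / √(0.8B² + 0.2W² + 0.7).

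With B = 0.5:
- W = 0: 0.40/√0.900 = 0.42
- W = 0.25: 0.45/√0.9125 = 0.47
- W = 0.50: 0.50/√0.950 = 0.51

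The 95% interval around 0.47 at n = 100 is tanh(atanh 0.47 ± 1.96/√97), or 0.30 to 0.61. It covers all three values, so baseline r hardly distinguishes no within-patient relationship from a strong one. Over the same values of W, r runs 0.27–0.38 for B = 0.3 and 0.54–0.62 for B = 0.7.

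**4. Precision available for change.** With yearly review, DCR since 2019 and collection from September 2023 to September 2024, a patient can have at most about 4–5 routine films plus the Part B film. The number of patients with repeat films is not given. For an assumed change correlation of 0.30, the same formula gives 95% intervals of 0.11–0.47 (100 patients), 0.09–0.49 (80) and 0.02–0.53 (50).

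**5. Part B film.** Same model, with 1–5 routine films plus one Part B film per patient, a time term, and a true within-patient slope of 0.50. Shifts are in units of total DCR SD, which is √(0.8 + 0.2) = 1. Ranges span slightly different fitted models.

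| Assumed shift on the Part B film | Shift ignored | Acquisition-type term added |
|---|---|---|
| 0.1 to 0.3, common to all | 0.50 to 0.48 | – |
| 0.5, common | 0.43–0.45 | 0.50 |
| 1.0, common | 0.31–0.35 | 0.50 |
| varies between patients, SD 0.3 | – | 0.46 |
| varies between patients, SD 0.5 | – | 0.41 |

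Routine films alone give about 0.50. The SD of that estimate is 0.067–0.069, against 0.055–0.058 on all films: 0.067/0.058 = 1.16 and 0.069/0.055 = 1.25, so 16–25% larger. In this set-up 80 of 100 patients have two or more routine films.

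**6. Form of the mixed model.** Assumed independent patient time slopes had SD 0 to 0.3 per year. A random intercept with model-based errors covered the true within-patient slope in 95.5% of datasets at slope SD 0, but only 88–89% at 0.3. Cluster-robust errors, or patient-specific slopes with time centred within patient, gave 94–96% throughout.

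**The case against.** The study calls itself exploratory and hypothesis generating, and the sentence on Part C analyses is worded to include rather than to limit. The baseline analysis is a legitimate answer to Aim 4. Because the markers come from continuing follow-up, it could also be prognostic, matching the rationale's question whether DCR features predict future outcomes. Step 3 tests only the same-visit reading. All this stands, and it lowers the weight of the point. It does not supply a method for change in DCR, which is the aim as Part C states it.

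On the Part B film the objection is stronger. The phrase about current imaging, under a retrospective heading, could mean existing routine films. Recruitment Part B is the clearer statement that the Part B investigation is included. That it replaces the routine film is an inference from the radiation statement. The routine breathing manoeuvre and posture are not described, so no acquisition shift can be derived. A shift of 0.5 SD is also large beside visit-to-visit variation: 0.5/√0.2 is about 1.1 within-patient SDs.

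A reader might infer that the Part B film will distort Part C or create a false association. The documents do not support that. Under the assumed model, bias is negligible at small shifts and runs towards zero at larger ones. Nor do they support reading the paired tests as the planned Part C analysis, since those tests are not assigned to it.

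**Conclusion.** The mismatch between aim and analysis holds on the text alone and needs no assumption: Part C asks about change, names a baseline analysis, and no section gives a method that relates change in DCR to a marker. The severity is modest, because no stated result is wrong.

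The handling of the Part B film is a secondary gap. The plan says that the film is used but not how. Under the assumed model the effect on the within-patient slope is negligible up to a shift of about 0.3 SD. It becomes appreciable, towards zero, from about 0.5 SD, and some bias remains even with an acquisition-type term if the shift varies between patients. Whether any shift exists is unknown.

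All numerical results rest on assumed variances and slopes, and on DCR measured without error. With DCR measurement error of SD 0.2 or 0.3, a true slope of 0.50 was estimated at about 0.43 or 0.38 whichever way the films were handled.

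**What to change.** - **Keep the baseline analysis.** Define baseline as the first available routine DCR since 2019. Say whether the marker is read at the same visit (Aim 4) or later (prediction).
- **Add a model for change.** Use a linear mixed model of the repeated annual-review marker on each patient's mean DCR (between-patient), each film's deviation from that mean (within-patient), and time. Where film numbers permit, allow patient-specific slopes with time centred within patient. Otherwise use a random intercept with cluster-robust standard errors.
- **Name in advance** one lead DCR measure from the list under 'Dynamic Chest X-ray' and one lead marker. Report how many patients have two or more films.
- **State how the Part B film is used.** Include an acquisition-type term in the all-films model, note that it removes only a common shift, and report a sensitivity analysis on routine films only.

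The cost is wording and a little extra analysis in R, on films that Part C already intends to use. No visit, film or consent is added. The routine-only result will have a somewhat larger standard error (16–25% in the illustration), because patients with a single routine film no longer inform within-patient change.

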A physical anatomical marker (left/right) is manually added to the detector. Density is set to -2 on the control panel, and the dynamic study function selected. The tube filter is set at 1.0mm Al, 0.1mmCu (copper and aluminium). The SID (distance to detector) is set to 200cm. A 180cm focal distance grid (40L per cm, ratio 12:1, and 17 by 17 inch / 42.18cm x 42.18cm) is used. Exposure factors are set at tube voltage 100kVP, tube current 80mA, exposure duration 4.0ms. Collimation (the adjustment of the x-ray field size to the minimum needed to capture the required images for a specific patient) is performed as per a standard chest x-ray, usually around 40cm by 30cm. The patient is positioned in a posterior-anterior position.

The frame rate for those participants undergoing routine clinical imaging will be set at 15 frames per second (fps), the standard frame rate used clinically.

Breathing instructions are called out as per Spirometry instructions. The image capture is stopped once the breathing the spirometry action is complete (this can be completed in around 10s or 150 frames), or if the 220 frame limit is reached, whichever comes first. If the spirometry is suboptimal the procedure cannot be repeated.

Once the image capture/spirometry is complete, exposure factors are recorded by the operator, including the total number of frames and total duration in seconds.

The images captured are transferred to the local PACS server as well as an NHS server. Images are then downloaded from the NHS server onto a secure workstation for analysis in the research department. Images are anonymised to comply with data protection policies. Images are then processed using Konica Minolta DI-X1 software and re-uploaded to the server.

The images acquired by the DCR are processed using the Di-X1 machine using the computer algorithms. Further updates to the machine may allow further analysis. Key quantitative measures derived from the D1-X1 analysis of the DCR currently include:

1. Diaphragmatic excursion – maximal inspiratory and expiratory in mm
2. Peak diaphragm velocity
3. Peak diaphragm velocity at inspiration / expiration
4. Peak distance from apex to diaphragm
5. Lung field area during range of maximal inspiration / expiration – as calculated by Konica Minolta software. Reviewed individually to ensure algorithm accurately detecting lung field area.

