The Figure below demonstrates the room set up. The study volunteer attends room 2 where our DCR machine in LHCH is placed. The individual sits on a stool facing the FPD. The Radiographer, researcher and any pulmonary physiologist are by the control station. The volunteer holds the spirometer to their mouth. When instructions for Spirometry are given the Radiographer presses the button to record the DCR. The complete spirometry attempt is completed, and the x-ray ceased when the full motion completed. The DCR machine will stop after 220 frames the exposure will not continue if the full spirometry is not completed.

Sample and Recruitment

This study is exploratory work and is ultimately hypothesis generating and as such no formal statistical power calculation has been carried out. Target recruitment numbers are therefore based on pragmatic assessment of the ability to recruit and measure successfully.

Recruitment Part A: The study involves the recruitment of healthy volunteers from general population. We would aim to recruit n=100 participants. Recruitment will be made through internal advertisement at LHCH hospital trust, University of Liverpool and Liverpool John Moore University

Recruitment Part B: People for part B of the study will be recruited through annual review process at CF clinic. As part of this process all people will undergo DCR and spirometry. They will be exposed to no further radiation, but it will mean that they have to perform an extra spirometry procedures. Individuals participating in part B will consent to using their investigation in part of the longitudinal review.

The Liverpool Heart and chest hospital has approximately 350 people with CF, however only 302 are present in the area (as opposed to being based in other areas which means they don't come to clinic). Transplanted individuals will be excluded (totalling 7) as well as pregnant individuals (currently 15). There is approximately 20% exacerbation rate and approximately 30% do not attend any given appointment. This would give us a projected population of just over 150 individuals to recruit from (please see Figure 2 below).

It is important to note that this is a conservative estimate pwCF who have a current exacerbation or who DNA appointment may return for their annual review study at a later date (however this may not be within the study recruitment period)

[figure not shown]
Consent

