Informed consent will be obtained prior to the participant undergoing enrolment in the study. A patient information sheet will be provided prior to taking informed consent.

The opportunity to ask questions will be given. Capacity will be assessed in order to determine that informed consent can be given.

Participation will be voluntary, and consent can be withdrawn at any time.

Figure 2 - CF cohort selection flow chart

Participation enrolment criteria:**Part A: Real-time paired DCR and Spirometry in Healthy control Group****Inclusion criteria:**

- Age: ≥ 17 years old and ≤ 50 years old
- and
- No underlying respiratory illness (chronic or acute)
- and
- Able to provide informed consent

Exclusion criteria**General exclusion criteria:**

Any of:

- Potentially pregnant or lactating
- Inability to provide informed consent
- Unable or unwilling to sit to perform DCR/Spirometry in the radiology department
- Unable or unwilling to follow Spirometry breathing instructions (e.g., holding breath or taking a deep breath)
- Unable to perform reproducible spirometry and/or full pulmonary function studies within ATS-ERS criteria
- Significant radiation exposure within the last year (for example, numerous CT scans of chest)
- Involved, either currently or recently, in other studies involved non-routine exposure to sources of ionising radiation
- Any serious or active medical or psychiatric illness, which in the opinion of the investigators, would interfere with subject treatment, assessment, or compliance with the protocol
- Inability to complete spirometry performance in 20 seconds.
- Current Chest infection

Spirometry exclusion criteria

Any of:

- Unstable cardiovascular status, recent MI or PE (within 6 weeks)
- Haemoptysis of unknown aetiology (within 6 weeks)
- Pneumothorax (present, or occurring within 6 weeks)
- Within 24 hours of bronchoscopy
- Thoracic, abdominal or cerebral aneurysm
- Recent eye surgery or increased intraocular pressure
- Recent thoracic or abdominal surgery
- Acute nausea, vomiting or diarrhoea
- Pregnancy
- Undergoing treatment for TB

- **Part B: Real-time paired DCR and spirometry in a CF subgroup**

Inclusion criteria:

- Age: ≥ 17 years old ≤ 50
and
- Attending the adult CF Unit at LHCH
and
- Confirmed CF diagnosis (positive sweat test in childhood and by genotyping)
and
- Able to provide informed consent

Exclusion criteria**General exclusion criteria, same as Group A (see above) plus:**

- Recipient of Lung transplant

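### Minor: the 20 s eligibility limit does not match the 220-frame capture stop (14.7 s at 15 fps), and the analysis plan does not say how to handle a capture that reaches the stop

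*Combined protocol and SAP*

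**What the plan says.** The general exclusion criteria under Participation enrolment criteria rule out "Inability to complete spirometry performance in 20 seconds". Part B adopts the same general criteria, so the limit covers the CF group too.

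The Dynamic Chest X-ray section gives a frame rate of 15 per second, in a sentence worded for participants having routine clinical imaging. It ends capture when the manoeuvre is finished "or if the 220 frame limit is reached, whichever comes first", and says of the manoeuvre that "this can be completed in around 10s or 150 frames". The room set-up text confirms that the stop is hard: "The DCR machine will stop after 220 frames the exposure will not continue if the full spirometry is not completed". On timing it says "When instructions for Spirometry are given the Radiographer presses the button to record the DCR"; the Spirometry section adds that the investigator tells the radiographer when to begin. On repeats: "If the spirometry is suboptimal the procedure cannot be repeated".

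The operator records the exposure factors, "including the total number of frames and total duration in seconds". The key DCR measures include expiratory diaphragm excursion and "Lung field area during range of maximal inspiration / expiration". The Statistical analysis section does not mention the frame count or a capture that reaches the stop.

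**The concern.** Two stated limits govern the same manoeuvre and do not agree. Followed as written, the protocol can admit someone whose exhalation outlasts the capture. For that person, the DCR measures that depend on end-expiration may be read too early, while the spirometer goes on to record a full FVC. The pair is then no longer like for like, although simultaneous measurement is what the protocol offers as its advance over sequential testing.

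For a healthy volunteer there is a second cost. The Ionising Radiation section describes their exposure as additional to normal care, so an incomplete capture that could have been foreseen is worth avoiding. FEV1 and the inspiratory and early-expiratory DCR measures should be little affected.

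**Working it through.** **Inputs from the protocol.** Frame rate 15 per second; stop at 220 frames; eligibility limit 20 s; typical manoeuvre about 10 s or 150 frames; Table 3 minimum expiration 6 s (or to a plateau), with no maximum.

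**Reproducing the protocol's figure.** Frames = rate × seconds = 15 × 10 = 150, as stated.

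**The two limits on one scale.**
- Capture stop: 220 / 15 = 14.67 s.
- Eligibility limit: 20 × 15 = 300 frames.
- Gap: 300 − 220 = 80 frames = 5.33 s.
- Margin for the typical manoeuvre: 220 − 150 = 70 frames = 4.67 s.

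**Expiration that fits.** The time from the start of recording to the onset of expiration is not given. Assuming 2 to 4 s, 14.67 − 2 = 12.67 s down to 14.67 − 4 = 10.67 s of expiration is captured. Both exceed the 6 s in Table 3, so only long expirations are cut.

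**Does anything else close the gap?**
- Table 3 and the reproducible-spirometry criterion set no upper limit on duration.
- The individual image review checks that the software detects the lung field correctly, not that the capture is complete.
- No repeat is provided for a truncated DCR.
- The frame count is recorded, but no analysis rule uses it.

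**Possible loss per person (illustration only).** Assume single-exponential emptying with time constant τ, a 4 s lead and a 20 s manoeuvre, so that expiration lasts 16 s and 10.67 s of it is captured.
- FEV1/FVC = (1 − e^(−1/τ)) / (1 − e^(−16/τ)).
- Uncaptured share = 1 − (1 − e^(−10.67/τ)) / (1 − e^(−16/τ)).

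| τ (s) | FEV1/FVC | FVC uncaptured |
|---|---|---|
| 1.5 | 0.49 | 0.08% |
| 2.0 | 0.39 | 0.45% |
| 3.9 | 0.23 | about 5% |

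On an assumed FVC of 3 to 4 L, 0.45% is about 14 to 18 mL, roughly a tenth of the 0.150 L repeatability tolerance in Table 3. Reaching 0.150 L of a 3 L FVC (5%) needs τ near 3.9 s, which is very severe obstruction. A slower, non-exponential tail could lose more, but the documents give no data on that.

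**The case against.** The strongest reply is that the protocol discloses the stop twice, that neither number is miscalculated, and that the 20 s criterion concerns spirometry rather than promising 20 s of imaging. It also defines no starting point, so placing both limits on one clock is an interpretation. That is fair, but it does not close the gap. If the 20 s means expiration alone, the mismatch is wider, because inspiration also uses frames. Disclosing the stop does not say what becomes of the data.

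A second reply is that 15 frames per second is stated only for routine imaging. This stands as a caveat. It is the likely rate for healthy volunteers too: the paired-procedure section says Parts A and B follow the same process, the dose estimate uses 15 per second, and no other rate appears. The mismatch would disappear only at 220 / 20 = 11 per second or slower.

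A third reply is that the effect is probably small in an exploratory study of people aged 17 to 50 without a current exacerbation. This stands, and it is why the point is minor.

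Three stronger readings are tempting, and the documents support none of them.
- *Truncation falls more heavily on CF and biases the comparison with healthy volunteers (aim 3).* This is plausible, but no manoeuvre times are given for either group.
- *Every capture that reaches 220 frames is spoiled and should be excluded.* A plateau may come before the stop, and exclusion would selectively remove the slowest exhalers.
- *The 0.24 mSv dose is wrong because it assumes up to 20 s.* A 220-frame capture is shorter than that, so the figure is a conservative upper bound.

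**Conclusion.** The plan is wrong as written on a minor point. Eligibility allows a manoeuvre 5.3 s (80 frames) longer than the capture can follow, and no rule covers the resulting data. The arithmetic is firm for CF participants and rests on the likely 15 frames per second for healthy volunteers. How many people are affected is unknown and may be zero. The loss per person is probably small, judged by an illustrative model with an assumed lead time and emptying pattern. Only end-expiratory DCR measures paired with FVC are at issue. The study as a whole is not threatened.

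**What to change.** 1. **Eligibility and procedure.** Replace 20 s with about 14.7 s, counted from the instruction that would start recording to the end of expiration. The spirometry-only attempts have no recording of their own, so that instruction serves as the start point. Check the limit on those two attempts, and do not image healthy volunteers who exceed it. CF participants who exceed it may be kept, because their DCR is routine care.
2. **Data check.** Flag captures whose recorded frame count reaches 220. Use the simultaneous volume-time trace to see whether material volume was exhaled after the last frame, and define material in advance.
3. **Analysis.** Keep flagged captures in the main analysis and report their number by group. Run a sensitivity analysis of expiratory diaphragm excursion and lung field area at maximal expiration without the captures shown to be materially truncated.

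Raising the stop to 300 frames or slowing to 11 per second would also align the limits. However, the documents do not show that the stop can be raised, and 11 per second departs from the clinical standard rate.

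**Cost.** A few sentences, one timing to note on the practice attempts, and no added visits or radiation. A few healthy volunteers may not be imaged. Screening would then differ between groups, which must be reported with the aim 3 comparison. The sensitivity analysis loses little precision: with the Fisher-z standard error 1/√(n − 3), dropping 5 or 10 of 100 pairs (illustrative numbers) raises it from 0.1015 to 0.1043 (+2.7%) or 0.1072 (+5.6%).
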